9.2. PROTOCOL DEVIATIONS

Number and percentage of participants with important protocol deviations, as identified by the study team in a blinded fashion before the DBL, will be provided overall and by planned treatment group based on the FAS for each category of protocol deviations specified in the Protocol Deviations Management Plan.

A listing of protocol deviations identified by the study team (important or not) will be provided.

10. DEMOGRAPHIC AND OTHER BASELINE CHARACTERISTICS

The following demographic and other baseline characteristics will be reported for this study:

- Age (years) collected at informed consent
- Age groups (≥18 to <60 years, ≥60 to <70 years, ≥70 to <80 years, and ≥80 years; ≥60 years, ≥65 years, and ≥75 years)
- Sex (refer to Section 7.7)
- Race (refer to Section 7.7)
- Ethnicity (refer to Section 7.7)
- Weight (kg)

- Height (cm)
- Body Mass Index (BMI) (kg/m²)
- BMI group (kg/m^2) $(<18.5, \ge 18.5 <25, \ge 25 <30, \ge 30 <40, and \ge 40)$
- Screening result from NP swab for SARS-CoV-2 RT-PCR (positive, negative)
- Smoking status (current, former, never)
- ECOG performance status (0, 1, and >1)
- Home or other confinement status (yes/no)
- Country (refer to Section 7.7)
- High Risk for severe COVID-19 at baseline (History of Obesity, Obese (baseline BMI≥30), Morbid Obesity (baseline BMI≥40), CKD, Diabetes, Immunosuppressive disease, Immunosuppressive treatment, CV Disease, COPD, chronic liver disease, Hypertension, Asthma, Cancer, Smoking, Sickle cell disease) (yes/no)
- COVID-19 risk assessment data as collected on the eCRF
- Subgroups specified in Section 7.7 and not previously listed above

Continuous demographic and other baseline characteristics will be summarized using descriptive statistics overall and by planned treatment group based on the FAS and FPAS. For categorical demographic and other baseline characteristics, number and percentage of participants in each category will be provided overall and by planned treatment group based on the FAS and FPAS. If there are major differences between the FAS and the SAF, the summaries will be repeated and presented by actual treatment group for the SAF. No statistical testing will be carried out for demographic or other baseline characteristics.

All demographic and risk assessment data will be listed.

10.1. DERIVATIONS

BMI, in kg/m², will be calculated as follows:

• BMI (kg/m^2) = weight $(kg)/[height (m)^2]$

11. MEDICAL HISTORY

Medical history is defined as any medical conditions/diseases that started and stopped before the first dose of IMP.

Medical history will be coded using the Medical Dictionary for Regulatory Activities (MedDRA), version 23.1 or higher, and will be summarized by System Organ Class (SOC) and Preferred Term (PT) overall and by planned treatment group based on the FAS. A participant having more than one medical condition/disease within the same

SOC/PT will be counted only once for that SOC or PT.

COVID co-morbidities are collected on the Medical history page of the eCRF. The number and percentage of participants with each co-morbidity and also with any co-morbidities will be summarized overall and by planned treatment group based on the FAS.

All medical history will be listed.

12. CONCOMITANT ILLNESSES

Concomitant conditions/illnesses are defined as any medical conditions/illnesses that started before the first dose of IMP AND were ongoing at the time of the dose of IMP or ended on date of dose.

Concomitant conditions/illnesses will be coded using the MedDRA, version 23.1 or higher, and will be summarized by SOC and PT overall and by planned treatment group based on the FAS. A participant having more than one medical condition/illness within the same SOC or PT will be counted only once for that SOC or PT.

All concomitant conditions/illnesses will be listed.

13. MEDICATIONS

Prior medications are defined as any medication that started and stopped prior to the dose of IMP.

Concomitant medications are defined as:

- Any medication that started before the dose of IMP AND was ongoing at the time of the dose of IMP or ended
 on the date of dose of IMP;
- Any medication that started on or after the dose of IMP.

Partially or completely missing medication start and stop dates will be handled as described in APPENDIX 1.

All medications will be coded using the World Health Organization (WHO) Drug Global dictionary, version B3 March 2020, or a more recent version.

Prior and concomitant medications will be summarized by Anatomical Therapeutic Class (ATC) level 2 and preferred drug name overall and by planned treatment group based on the FAS. A participant having more than one medication within the same ATC Level 2 or preferred drug name will be counted only once for that ATC Level 2 or preferred drug name.

All collected prior and concomitant medications will be listed.

14. EXPOSURE TO STUDY INTERVENTION

Due to the simplicity of dosing for this study, exposure is summarized in the participant disposition table. All exposure data will be listed.

15. COMPLIANCE WITH STUDY INTERVENTION

Compliance will not be calculated since participants receive a single dose (2 IM injections) within clinic.

16. EFFICACY ENDPOINTS

Unless otherwise indicated, all efficacy summaries and figures will be presented based on the FPAS.

16.1. PRIMARY EFFICACY

16.1.1. PRIMARY EFFICACY ENDPOINT

The primary endpoint is the first case of SARS-CoV-2 RT-PCR-positive symptomatic illness occurring post dose of IMP and prior to Day 183. The primary efficacy endpoint is to be to be assessed after approximately 24 primary endpoint events have been confirmed or 30% of study participants have become unblinded, whichever occurs earlier.

Participants will be included as an event in the primary endpoint if they have RT-PCR-confirmed SARS-CoV-2 prior to Day 183 and present with at least one of the qualifying symptoms in Table M:. The onset of symptoms will commonly occur between 2 and 8 days of infection with detectable virus typically up to 15 days. To maintain the relationship between the RT-PCR sample and symptoms the sample should be collected on or close to the symptom assessment but must be collected within 5 days prior or 10 days following the assessment of qualifying symptoms. This duration will allow participants time to assess and confirm symptoms under medical supervision after the onset of symptoms, which will typically, but not always, occur at Illness Visit Day 1. A positive SARS-CoV-2 RT-PCR will be defined based on the central laboratory result whenever both central and local laboratory results are available for nasopharyngeal (NP) swabs, or if only a central lab NP swab result is available. If only a local NP swab laboratory result is available, then the local laboratory result will be used. If neither central nor local NP swab laboratory results are available, a saliva sample taken within window during Illness Visits will be used to determine the RT-PCR result. If no SARS-CoV-2 RT-PCR results are available, the participant will be considered as not having met the primary endpoint. Data from the eCRF will be used to determine if the participant met the qualifying symptoms. If a participant will be considered as not having met the primary endpoint.

Table M: COVID-19 Qualifying Symptoms

Duration	Symptom
	Fever
	Shortness of breath
	Difficulty breathing
No minimum duration	New onset confusion (only for participants ≥ 60 years old)
	Appetite loss or decrease food intake (only for participants ≥ 60 years old)
	Increased supplemental oxygen requirement (only for participants ≥ 60 years old on baseline supplemental oxygen)
Must be present for ≥ 2 days	Chills
	Cough
	Fatigue
	Muscle aches
	Body aches
	Headache
	New loss of taste
	New loss of smell
	Sore throat
	Congestion
	Runny nose
	Nausea
	Vomiting
	Diarrhea

Adapted from (CDC, 2020)

CDC, Centers for Disease Control and Prevention

16.1.2. MISSING DATA IMPUTATION METHOD FOR PRIMARY EFFICACY ENDPOINT

No missing data imputation method will be used for primary efficacy analysis. For participants who withdraw from the study prior to having met the criteria for the primary efficacy endpoint. Participants will be censored (considered as not having the event) at the time of last observation.

Sensitivity analyses will be explored to assess the robustness of treatment effects for the primary efficacy endpoint, where different missing data mechanisms will be explored using multiple imputation approaches. Full details of the sensitivity analyses are specified in Section 16.1.5.

16.1.3. PRIMARY ESTIMAND

The treatment condition of interest is single dose of AZD7442 (two IM injections, one for each mAb component, AZD8895 and AZD1061). The alternative treatment condition to which comparison will be made is a placebo.

The population of participants targeted in the primary estimand includes adults at least 18 years of age who have not had a prior SARS-CoV-2 RT-PCR-positive confirmed COVID-19 infection and who are candidates for benefit from passive immunization with antibodies, defined as having increased risk for inadequate response to active immunization (predicted poor responders to vaccines OR intolerant of vaccine), OR having increased risk for SARS-CoV-2 infection, defined as those whose locations or circumstances put them at appreciable risk of exposure to SARS-CoV-2 and COVID-19.

The primary endpoint (variable) to be obtained is a binary response, whereby a participant is defined as a COVID-19 case if their first case of SARS-CoV-2 RT-PCR-positive symptomatic illness occurs post dose of IMP prior to Day 183.

The primary estimand uses a while on treatment strategy. Data for participants who become unblinded to treatment assignment and/or take COVID-19 vaccine or other COVID-19 preventive product, in both cases prior to having met the criteria for the primary efficacy endpoint, are censored at the date of unblinding/receipt of first dose of COVID-19 preventive product, whichever is earlier.

The population-level summary measure is prophylactic efficacy, calculated as 1 – relative risk (RR). (RR is the incidence of infection in the AZD7442 group relative to the incidence of infection in the control group.)

16.1.4. PRIMARY ANALYSIS OF PRIMARY EFFICACY ENDPOINT

The primary efficacy analysis of the primary endpoint will be performed on the FPAS. Participants who withdraw from the study prior to having met the criteria for the primary efficacy endpoint will be censored (considered as not having the event) at the time of last observation. Participants with deaths that are caused by SARS-CoV-2 (death related to COVID marked on the death eCRF page) will be considered as having the event, even if no other qualifying symptoms are met. Participants with hospitalizations due to COVID-19 will also be considered as having the event.

A Poisson regression model with robust variance (Zou, 2004) adjusting for follow-up time, will be used as the primary efficacy analysis model to estimate the RR on the incidence of SARS-CoV-2 RT-PCR-positive symptomatic illness occurring post dose of IMP between the AZD7442 and the placebo groups. The model contains the planned treatment group and age group at the time of informed consent (i.e., ≥ 60 years and < 60 years, see Section 7.6) as a covariate. The logarithm of the participant's corresponding follow-up time at risk starting from dose up to the study day 183 visit will be used as an offset variable in the model to adjust for participants having different exposure times during which the events occur. Participants who withdraw or have a non-COVID-19 related death prior to meeting the primary endpoint will not be counted as having the event. The follow up time for those participants will be at that time relative to dose. Calculation of follow-up time is detailed as following:

- For participants who meet the primary endpoint before Day 183, the follow-up time will be calculated as (Date of Onset of Primary Endpoint) (Date of Dosing) + 1. Date of Onset of Primary Endpoint is defined as the assessment date of qualifying COVID symptoms, if associated with a positive SARS-CoV-2 RT-PCR lab test from a sample collected within the 5 days prior to symptom assessment through 10 days after symptom assessment. In the case of death due to COVID-19 or hospitalization due to COVID-19, the Date of Onset of Primary Endpoint is the earliest date of death/date of hospital admission when a qualifying symptom assessment is not observed.
- For participants who do not experience a primary endpoint before Day 183, the efficacy follow-up time will be considered censored and determined based on the following:
 - o If an end of study date occurs prior to Day 183, the efficacy follow-up time will be calculated as (Date of End of Study or Date of Last Assessment, whichever is later) (Date of Dosing) + 1.
 - o If an end of study date occurs after Day 183, the efficacy follow-up will be censored at Day 183.

For participants who continue to participate in the study at the time of the primary analysis, the DCO date will be used as their last assessment date. For participants with no post-baseline visit data available, the date of IMP administration will be used i.e. follow-up will be 1 day.

Efficacy is the incidence of infection in the AZD7442 group relative to the incidence of infection in the placebo group, expressed as a percentage. Efficacy will be calculated as relative risk reduction (RRR) = 100% x (1 - relative risk).

RRR and its corresponding 2-sided 95% CI will be estimated from the Poisson regression model with robust variance. In addition, the 2-sided p-value testing null hypothesis that there is no difference in efficacy between AZD7442 and placebo (i.e. the efficacy is equal to 0) will be obtained from the model. Statistical significance will be achieved if the lower bound of the 95% CI for efficacy is > 0, which corresponds to an observed two-sided p-value < 0.05. For the final analysis nominal 95% CI's will be presented.

The Poisson regression with robust variance analysis will be implemented by using the SAS PROC GENMOD procedure with the REPEATED statement for participant ID and logarithm link as well as OFFSET option. The estimated parameter $\hat{\beta}$ [i.e., log(RR)], 2-sided 95% confidence interval (CI) for $\hat{\beta}$, and the 2-sided p-value will be obtained from the SAS outputs. The estimated RR and corresponding CI for the RR is given by exponentiating $\hat{\beta}$ and its confidence limits. Therefore, the percent of RRR is given by $[(1 - \exp(\hat{\beta})) * 100\%]$. The CI for the percent of RRR is given by ([1 - exp(upper confidence limit for $\hat{\beta}$) * 100%], [1 - exp(lower confidence limit for $\hat{\beta}$) * 100%]).

If convergence cannot be achieved with the Poisson regression analysis model with robust variance, the Cochran-Mantel-Haenszel (CMH) will be used as the primary analysis model to test the treatment effect on SARS-CoV-2 RT-PCR-positive symptomatic illness between AZD7442 and placebo groups. The CMH test will be stratified by age group at the time of informed consent (i.e., ≥ 60 years and < 60 years, see Section 7.6). The RR of AZD7442 over placebo for the incidence of SARS-CoV-2 RT-PCR-positive symptomatic illness occurring post dose and the 95% CI will be obtained. The percent of RRR and the 95% CI will be reported following the relationship of RRR

(%) = (1- RR) * 100%. A Breslow-Day test will be conducted, and p-value presented, to evaluate homogeneity of the RRR across strata.

A listing will be provided for all COVID-19 symptom assessments and NP swabs assessed by RT-PCR (both local laboratory and central laboratory samples) regardless of RT-PCR result.

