4.2. MORBIDITY ADJUDICATION COMMITTEE

An independent Morbidity Adjudication Committee (MAC) will be constituted to provide an independent, external, systematic, and unbiased assessment of blinded data to evaluate whether the causes of death for participants are considered COVID-19 associated. Only adjudicated deaths will be included in efficacy endpoints. All fatal events will be further assessed as part of safety evaluation. Further details of this adjudication will be provided in a separate Morbidity Adjudication Committee Charter.

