4.4. PRIMARY ANALYSIS

The primary analysis will occur after approximately 24 primary endpoint events have been confirmed across the active and control groups or 30% of study participants have become unblinded (at which point the ability to observe primary endpoint events is expected to have diminished), whichever occurs earlier. All primary endpoint events accrued up until the data cut-off (DCO) will be included in the primary analysis. The date for the DCO for this analysis will be the date that the 24th primary endpoint event is confirmed or the date that 30% of study participants have become unblinded, whichever occurs earlier.

All planned primary analyses are detailed in this SAP and will be performed by AstraZeneca or its delegates following Sponsor authorization of this SAP, Sponsor authorization of the analysis sets, database lock (DBL), and

analysis team unblinding. The primary analysis will be carried out by an unblinded analysis team, and the procedure will be detailed in an unblinding plan; participant level unblinding information will be kept strictly confidential, and rationale for any unblinding will be documented.

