16.1.5. SENSITIVITY ANALYSES FOR PRIMARY EFFICACY ENDPOINT

As a sensitivity analysis to the handling of missing data in the analysis of the primary efficacy endpoint, the primary analysis of the primary efficacy endpoint (Section 16.1.4) will be repeated with multiple imputation for intercurrent events. For participants who are in FPAS but (1) do not have a SARS-CoV-2 RT-PCR-positive symptomatic illness status occurring post dose of IMP and withdraw from the study prior to the time of analysis, or (2) were unblinded to treatment assignment prior to having met the criteria for the primary efficacy endpoint, or (3) received COVID-19 vaccine or other preventive product prior to having met the criteria for the primary efficacy endpoint, their event status will be imputed assuming the observed event rate per treatment group conditional on stratification factors using multiple imputation techniques as described in the following paragraphs.

The primary analysis using Poisson regression with robust variance requires a participant-level dataset. A repeated imputation approach is introduced to impute the status of SARS-CoV-2 RT-PCR-positive symptomatic illness occurring post dose of IMP for missing observations at the participant level for the model fitting. By incorporating the between-imputation variance, a reliable statistical inference in both hypothesis testing and CI estimation of the treatment effect is expected through the repeated imputation (Little and Rubin, 2002). In the primary analysis the missing outcome for participants who drop out (e.g., withdrawal, lost to follow-up, death not caused by SARS-CoV-2, etc.) prior to reaching cut-off time for analysis without a SARS-CoV-2 RT-PCR-positive symptomatic illness occurring post dose of IMP will be imputed per stratum determined by the stratification factor using observed event rate per treatment group. The imputation and subsequent analysis may be carried out using SAS PROC MI (Monotone Logistic Regression Method) and SAS PROC MIANALYZE. The detailed imputation steps are described as follows.

- Step 1: Missing events in both arms will be imputed with the observed event rate per treatment group. The imputation may be executed using SAS PROC MI (logistic regression method with the recoded treatment term and stratification factor), or random sampling from an appropriate distribution. The random seed is 10021.

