16.1.9. KEY SUPPORTIVE ANALYSES OF PRIMARY EFFICACY ENDPOINT

As key supportive analyses, the primary analysis of the efficacy endpoint (refer to Section 16.1.4) will be repeated using two key supportive estimands: one, which utilizes a treatment policy strategy for intercurrent events, and a second, which includes death due to any cause in the primary endpoint. These analyses are included in the multiple testing hierarchy described in Section 7.4. The attributes of the key supportive estimands are described in Table O: and Table P:.

Table O: List of First Key Supportive Estimand Attributes

Label	The efficacy of a single IM dose of AZD7442 compared to placebo for the prevention of COVID-19 prior to Day 183 – Treatment Policy Estimand
Definition	Full pre-exposure analysis set, defined as all participants who were randomized, received
Population	at least one of the planned injections of IMP, and did not have a prior SARS-CoV-2 RT-
	PCR-positive confirmed COVID-19 infection. Targeted participants will have the
	following characteristics:
	Adults ≥ 18 years of age who are candidates for benefit from passive immunization with
	antibodies, defined as having increased risk for inadequate response to active
	immunization (predicted poor responders to vaccines OR intolerant of vaccine), OR

	having increased risk for SARS-CoV-2 infection, defined as those whose locations or circumstances put them at appreciable risk of exposure to SARS-CoV-2 and COVID-19.
Treatment Condition of Interest	Single dose of AZD7442 (× 2 IM injections, 1 for each mAb component) or placebo
Variable/Endpoint	A binary response, whereby a participant is defined as a COVID-19 case if their first case of SARS-CoV-2 RT-PCR-positive symptomatic illness occurs post dose of IMP and prior to Day 183.
Intercurrent event handling strategy	Participants who become unblinded to treatment assignment and/or take COVID-19 vaccine or other COVID-19 preventive product, in both cases prior to having met the criteria for the primary efficacy endpoint, will be included and analyzed regardless (i.e., intercurrent events will be handled using a treatment policy strategy).
Population-level summary measure	Prophylactic efficacy, calculated as 1-relative risk. (Relative risk is the incidence of infection in the AZD7442 group relative to the incidence of infection in the control group.)

Table P: List of Second Key Supportive Estimand Attributes

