16.3.1. EXPLORATORY EFFICACY ENDPOINTS

16.3.1.1. The Incidence of the First Case of SARS-CoV-2 RT-PCR-Positive Symptomatic Illness Occurring after Dosing with IMP through Day 366

An exploratory endpoint is the incidence of the first case of SARS-CoV-2 RT-PCR-positive symptomatic illness occurring after dosing with IMP through Day 366. The criteria for determining this endpoint is the same as those for the primary efficacy endpoint (see Section 16.1.1) except that the endpoint will only be evaluated within the specified efficacy evaluation period, through Day 366. The analysis will be performed on the full pre-exposure analysis set. This endpoint will be analyzed as described in Section 16.2.1.

To assess the durability of efficacy analyses for the incidence of the first case of SARS-CoV-2 RT-PCR-positive symptomatic illness occurring after dosing with IMP through Day 366, single-arm descriptive summaries over the Day 366 follow-up period for participants who received AZD7442 with no censoring for unblinding intercurrent events will be presented. However, if a participant receives a COVID-19 vaccine or COVID-19 preventive product, their follow-up will be censored at the date of first administration of that product.

16.3.1.2. Viral Genome Copies in NP Swabs Collected at Illness Visits as Determined by qRT-PCR

An exploratory efficacy endpoint is the viral genome copies in NP swabs which will be collected via SARS-CoV-2 RT-PCR test at central laboratory at Illness Visits as described in protocol section 1.3. The analysis will be performed on the full pre-exposure analysis set. Observed and change from baseline for Illness Visits (as defined in Section 6.5) in viral load will be summarized by planned treatment group and time points for the Illness Visits. A

logistic regression analysis of the proportion of participants with viral load $>10^4$ copies/mL may be performed. In addition, the number of weeks of high viral load ($>10^4$ copies/mL) among participants may be performed using a Stratified Wilcoxon rank sum test.

A listing will be provided for all viral genome copy data, regardless of RT-PCR result. Indicators will be included in listings of illness visits to distinguish those with positive RT-PCR results from those with negative RT-PCR results.

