18.2. DEATHS

If any participants die during the study as recorded on the "Death Details" page of the eCRF, the number and percentage of participants with death related to COVID-19 and those with other deaths will be summarized by actual treatment group based on the SAF. The number and percentage of participants with death related to COVID-19 as adjudicated by the MAC will also be summarized by actual treatment group based on the SAF.

A listing of all deaths will be provided.

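### Two SAP sections name different sources for deciding which deaths count as primary events: MAC adjudication (4.2) or the eCRF mark (16.1.4)

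*SAP*

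**What the plan says.** The SAP covers the parent PROVENT study. Its provisions on attributing deaths are these:

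- **SAP 4.2** sets up an independent MAC that works on blinded data to decide whether a death is COVID-19 associated, and then states: "Only adjudicated deaths will be included in efficacy endpoints".
- **SAP 16.1.4**, the operational definition for the primary analysis, says that participants with "deaths that are caused by SARS-CoV-2 (death related to COVID marked on the death eCRF page) will be considered as having the event". This applies even without other qualifying symptoms. COVID-19 hospitalizations also count. A non-COVID-19 death is a non-event, and the source for that classification is not named.
- **SAP 16.1.5** imputes outcomes for "participants who drop out (e.g., withdrawal, lost to follow-up, death not caused by SARS-CoV-2, etc.) prior to reaching cut-off time", again without naming the source of the attribution.
- **SAP 18.2** summarizes deaths from the eCRF death page and adds: "The number and percentage of participants with death related to COVID-19 as adjudicated by the MAC will also be summarized by actual treatment group".
- **SAP 4.4** ties the cut-off to the event count: "The date for the DCO for this analysis will be the date that the 24th primary endpoint event is confirmed", or the date on which 30% of participants are unblinded if that is earlier.

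The endpoint and primary estimand text (16.1.1, 16.1.3, Table A) does not mention death.

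**The concern.** Sections 4.2 and 16.1.4 give different data sources for the same primary event. Because 18.2 reports both, the eCRF mark cannot be shorthand for the MAC's verdict. Two analysts following the SAP could therefore count different primary events, and the count also feeds the data cut-off.

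Blinding is the second issue. In the primary estimand, participants who are unblinded or take a preventive product "are censored at the date of unblinding/receipt of first dose of COVID-19 preventive product, whichever is earlier". Knowledge of treatment can therefore affect attribution there only when a death precedes unblinding and its eCRF page is completed afterwards.

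The first key supportive estimand is more exposed. Under it such participants "will be included and analyzed regardless (i.e., intercurrent events will be handled using a treatment policy strategy"), so a site may attribute a death knowing the assignment, whereas the MAC sees blinded data. This estimand is second in the testing hierarchy (SAP 7.4) and gates the all-cause-mortality and key secondary tests. The Day 366 exploratory endpoint takes over the same rule: "The criteria for determining this endpoint is the same as those for the primary efficacy endpoint". The all-cause-mortality estimand does not depend on attribution.

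**Working it through.** **1. Which deaths are affected.** Under 16.1.1 and 16.1.4 a participant becomes a primary event by any of three routes: RT-PCR-positive symptomatic illness, COVID-19 hospitalization, or COVID-19 death. The first two need no attribution of death. The conflict therefore bites only when the eCRF and the MAC disagree and neither of the other routes is met.

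**2. Possible readings of the two sections together.**

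| Reading | Death counts if |
|---|---|
| 16.1.4 as written | eCRF mark is yes |
| 4.2 replaces the eCRF | MAC verdict is yes |
| 4.2 filters the eCRF | both are yes |

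These give different event sets whenever the sources disagree, and neither section refers to the other.

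**3. Inputs for the size.** AZD7442 n = 3433, placebo n = 1717, 80% efficacy, two-sided 5% level (SAP 7.1, 7.3); 24 events (SAP 4.4). Assumptions: equal follow-up in both arms and no covariate adjustment.

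With a events on AZD7442 and b on placebo:

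- RR = (a/3433)/(b/1717); efficacy = 1 − RR
- SE(log RR) = √(1/a − 1/3433 + 1/b − 1/1717)
- 95% CI for RR = exp(log RR ± 1.96 SE)

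*Check against the SAP's own figure.* With the total fixed at 24 and split binomially with probability 2×0.2/(2×0.2+1) = 0.286, simulated power using this variance is 97.9%. Table L gives 98%.

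**4. Expected case.** 24 × 0.286 = 6.9, so about 7 vs 17. RR = (7/3433)/(17/1717) = 0.206 and SE = 0.448.

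| AZD7442 vs placebo | Efficacy | 95% CI |
|---|---|---|
| 7 vs 17 | 79.4% | 50.4 to 91.4 |
| 7 vs 16 (one placebo death dropped) | 78.1% | 46.9 to 91.0 |
| 8 vs 17 (one AZD7442 death added) | 76.5% | 45.6 to 89.8 |

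The shift is 79.4 − 78.1 = 1.3 or 79.4 − 76.5 = 2.9 points.

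**5. Boundary case.** Every 24-event split was checked for loss of significance after dropping one placebo event or adding one AZD7442 event. Only 11 vs 13 flips.

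| Split | Lower bound | One placebo event dropped | One AZD7442 event added |
|---|---|---|---|
| 11 vs 13 | 5.7% | −3.7% (11 vs 12) | −1.0% (12 vs 13) |
| 10 vs 14 | 19.7% | 12.4% (10 vs 13) | 13.6% (11 vs 14) |

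**6. How likely 11 vs 13 is.** Binomial(24, q), with q = (1−VE)×3433/((1−VE)×3433 + 1717):

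| True efficacy | q | P(11 of 24 on AZD7442) |
|---|---|---|
| 80% | 0.286 | 3% |
| 70% | 0.375 | 11% |
| 60% | 0.444 | 16% |

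This is the probability of the split alone. A reversal also needs a death of the kind in step 1, reclassified in the adverse direction, so it is less likely than these figures.

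**7. Reported result.** Protocol 2.3.2 gives 25 cases and 77% (46 to 90). An 8 vs 17 split is inferred, not stated; it yields 76.5% (45.6 to 89.8). Protocol 2.3.1 reports 2 deaths, both among the severe placebo cases. Dropping both gives 8 vs 15: 73.3% (37.2 to 88.7), still significant.

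Steps 4 to 6 hold the cut-off fixed. A reclassification before the 24th event could instead move the cut-off date. The treatment-policy analysis may have a different event total, so these figures do not size it.

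**The case against.** The best reply is that the word *only* in 4.2 already governs: the eCRF page identifies a candidate death and adjudication then filters it. The SAP's revision summary lists the MAC as an addition, so the eCRF phrase may be left over. That is plausible, but the SAP does not say it. Filtering is also a different rule from replacement, and an analyst following 16.1.4 as written would break 4.2.

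The MAC Charter and the parent protocol were not available, and either may contain a rule. That limits the statement about precedence to the documents at hand, but it does not remove a contradiction within the SAP.

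Several narrower points stand:

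- The non-COVID-19 deaths in 16.1.4 and 16.1.5 are complements of the same definition, so they are not separate defects.
- 4.4 speaks of confirmed events, which suggests that a death awaiting adjudication would not count.
- At 25 events no split loses significance from one death: 11 vs 14 falls only to a lower bound of 5.7% (11 vs 13) or 7.5% (12 vs 14). A 12 vs 13 split (−1.0%) could gain it.
- If the two reported placebo deaths met the SAP 16.2.3.1 definition of a severe case, they already count as RT-PCR-positive symptomatic illness.
- The 18.2 tables would make disagreement between the sources visible.

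These points bear on size. They do not tell an analyst which source to use.

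**Conclusion.** The concern holds. The SAP names two sources for COVID-19 death as a primary event, and nothing supplied ranks them. The effect is usually small: 1 to 3 points for one death at the expected split, with significance lost only at 11 vs 13 among 24-event splits. Nothing here suggests that the reported result would reverse.

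It should be fixed because it concerns the definition of the primary event and feeds the cut-off. It also leaves a gated confirmatory test open to attribution that may not be blinded. The figures assume equal follow-up, no covariate adjustment and a fixed cut-off; how often the two sources would disagree is unknown.

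**What to change.** In SAP 16.1.4, replace the parenthesis that points to the death eCRF page with: (adjudicated by the MAC as COVID-19 associated). Use the same source for non-COVID-19 deaths in 16.1.4 and for deaths not caused by SARS-CoV-2 in 16.1.5. Keep the eCRF attribution as a sensitivity analysis.

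It would also help to state that the treatment-policy estimand and the Day 366 endpoint follow the same rule, and whether a death awaiting adjudication counts toward the 24-event trigger. The onset-date rule for a death that counts can stay as it is.

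The cost is one phrase plus short cross-references. Adjudication is already planned, and both classifications are already tabulated under 18.2.
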